### **7.3 Duration of Participation**

The patient will remain in the study until their telephone postoperative visit occurring within 14 days from discharge from the hospital.

### **7.4 Test Article(s) (Study Drug(s) and/or Study Device(s))**

#### **7.4.1 Description**

Ropivacaine Hydrochloride injection 0.2% is FDA approved for use in surgery as a field block (infiltration) regional anesthesia. We will use the Penn State Health standard of care ambulatory pump to provide the automatic and demand boluses of the study drug through the ESP catheters.

#### **7.4.2 Treatment Regimen**

Group	Drug mixture
ESPB	Ropivacaine 0.2%
SESPB	Normal saline

#### **7.4.3 Method for Assigning Subject to Treatment Groups**

On the working day prior to surgery, subjects consented for the study will be randomized from a computer-generated randomization list using SAS software (SAS Institute, Cary, NC) and using block stratification with block sizes of two and four to allow an equal number of participants in each of the study groups.

#### **7.4.4 Subject Compliance Monitoring**

Members of the research team will verify that the label on the study drug that they receive in the SDU matches the study ID and patient's specific randomization ID on their study bracelet.

#### **7.4.5 Blinding of the Test Article**

The study drugs will be prepared and provided by the investigational pharmacy who will be unblinded in this study. Post randomization of study patients (randomization will occur the working day prior to scheduled operative date), the study drug will be packaged in a cartridge which will be nonspecific to the medication type (Ropivacaine or Normal saline). The cartridge will be labeled both with the study ID and the patient's specific randomization number.

## **7.4.6 Receiving, Storage, Dispensing and Return**

### **7.4.6.1 Receipt of Test Article**

The Investigational Drug Service Pharmacy will maintain a study-specific supply of ropivacaine and normal saline for this study.

### **7.4.6.2 Storage**

The investigational pharmacy will handle storage and distribution of study drugs according to their approved handling protocols.

### **7.4.6.3 Preparation and Dispensing**

Following randomization of study patients (randomization will occur the working day prior to scheduled operative date), the study drug will be packaged both in a syringe which will contain the initial bolus dose and also in a cartridge which will contain the automatic pump boluses. Both the syringe and cartridge which will be nonspecific to the medication type (Ropivacaine or Normal saline). The syringe and cartridge will be labeled both with the study ID and the patient's specific randomization number. The ESPB syringe and cartridge will contain Ropivacaine 0.2% and the SESPB syringe and cartridge will contain normal saline. All preparation, dispensing of drug into cartridges and cartridge labeling will occur by the investigational pharmacy, who will remain unblinded. The day of surgery, a member of the research team will pick up both the syringe and cartridge and deliver it to the SDU. Here, the syringe followed by the cartridge will be connected to the block catheters allowing administration to begin in the SDU.

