#### 7.2.3 Day of Surgery - Pre-op

**In the SDU**, [name] will be present to ensure the current surgery and anesthesia team for the study patient are sufficiently educated on the protocol requirements and to ensure safety and protocol adherence. The patient will receive a study bracelet with the study ID and patient's specific randomization ID. The block procedure will be performed in the SDU by a member of the anesthesia block team, who is also part of the research team. The placement of the erector spinae catheter will occur according to standard practice guidelines using strict sterile conditions and is similar regardless of type of study medication that the patient will be randomly receiving. After the block catheter is placed, a member of the research team will pick up the study drug from the pharmacy, deliver it to the SDU and ensure the correct coordination of study drug to the patient using the patient's study ID bracelet. The ESP catheters will be bolused with 20 ml of Ropivacaine 0.5% vs 20ml of normal saline (placebo). Following this initial bolus, the ESP catheter will be connected to a pump containing Ropivacaine 0.2% or normal saline which will

deliver automatic boluses of 15ml of either study medication or normal saline every 3 hours. The automatic bolus dosing of 0.2% Ropivacaine is based on the standard dosing for all adults weighing between 50-120kg.

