#### **7.2.5 Postoperative hospital stay**

As per standard of care, the patient will be taken to the post anesthesia care unit (PACU). Here, [name] will be present to ensure the PACU team for the study patient are sufficiently educated on the protocol requirements and to ensure safety and protocol adherence. The ESPB pump will be delivering the automatic boluses of study drug (15ml every 3 hours) and additionally allow the patient to self-administer an on demand dose of study drug (0.2% Ropivacaine vs. normal saline) 5ml every 30 minutes throughout their hospital stay. The pump will permanently lock out and cease administration of both the automatic and self-administered boluses if the total dose of study drug reaches 770mg. The patient will still be able to initiate a demand dose, but no medication will be provided. If a lock out occurs prior to POD3, when the pump is scheduled to be removed, it will remain in place until the schedule day of removal. In the PACU, if the patient has additional pain requirements beyond the patient's previously determined acceptable pain score (asked pre-operatively per hospital standard) the PACU team may start a patient controlled analgesia (PCA) containing a set demand dose of hydromorphone 0.2mg every 6 mins. The pump will lock out if the maximum dose of 2mg per hour is reached. Bolus IV dosing of hydromorphone may be administered at the start of the PCA and throughout the hospital stay if deemed necessary by the treating physician team to control patient pain needs. One gram of acetaminophen IV every 8hrs will also be started in the PACU and continued through the patient's hospital stay. Acetaminophen will be converted over to oral regimen on POD 1. When transferred to the inpatient wards, [name] will ensure the nurse assigned to the study patient is aware and properly educated on the protocol requirements on a daily basis. She will also monitor for subject safety and protocol adherence while the study patient remains in the hospital by both identifying the patient room as on a research study as well as through daily interaction with the nursing team. While on the inpatient wards, additional pain control adjuncts will be provided using oral oxycodone 5-10mg every 4 hours administered based on a pain scale: pain 3-6 translates to 5mg tab and pain 7-10 translates to a 10mg tab. The PCA, as outlined above, may be started later in the hospital course, if needed, based on the patient's needs. The ESP block will be discontinued between 6AM-9AM on POD 3. Specific research order sets for this study will be created by the principal investigator for use of the study drug/placebo, narcotics and acetaminophen. All medications and dosages administered during the hospital stay (PACU and inpatient ward) will be reviewed and documented by a member of the research team to tabulate the total IV and oral opioid and study drug requirement of all study patients. Daily pain scales using the Visual analogue scale (VAS) 0-10 will be provided to the patient by a member of the research team, each morning between 9AM-12PM, on POD 1, 2 and 3 (scale attached). Additionally, on POD 1, between 9AM-12PM, a brief patient satisfaction survey (which has been previously validated (11)) will be provided to the patient to complete by a member of the research team (document attached).

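### The active arm's starting bolus is 0.5% ropivacaine in section 7.2.3 (100 mg in 20 ml) but 0.2% in section 7.4.6.3 (40 mg at the same volume)

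*Combined protocol and SAP*

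**What the plan says.** Section 7.2.3 (Day of Surgery - Pre-op) sets the starting dose: "The ESP catheters will be bolused with 20 ml of Ropivacaine 0.5% vs 20ml of normal saline (placebo". Its next sentence moves to a separate product for maintenance: "Following this initial bolus, the ESP catheter will be connected to a pump containing Ropivacaine 0.2% or normal saline". Bolus and pump are thus given different strengths on purpose.

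Section 7.4.6.3 (Preparation and Dispensing) describes the packaging. The study drug is "packaged both in a syringe which will contain the initial bolus dose and also in a cartridge which will contain the automatic pump boluses". It then gives the contents: "The ESPB syringe and cartridge will contain Ropivacaine 0.2% and the SESPB syringe and cartridge will contain normal saline". No volume is stated there.

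Two other sections describe the drug. Section 7.4.1 begins "Ropivacaine Hydrochloride injection 0.2% is FDA approved for use in surgery" and mentions no other strength. The regimen table in section 7.4.2 lists only 0.2% for the active arm. Neither gives a bolus strength or volume.

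**The concern.** Both statements are current text about the same item, the syringe injected before the pump is connected. Section 7.4.6.3 names the syringe explicitly, so its 0.2% cannot be read as referring to the cartridge alone. A pharmacist who follows that section and an anesthesiologist who follows section 7.2.3 would expect different doses.

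Three things are at stake:

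- **Definition of the intervention.** The loading dose is part of what the trial tests, and a report of the result has to state it.
- **Safety.** Section 11.0 lists local anesthetic toxicity among the risks, so whoever assesses that risk needs to know the starting dose.
- **Detection.** The bedside check in section 7.4.4 is to "verify that the label on the study drug that they receive in the SDU matches the study ID" and the randomization ID on the bracelet, and the syringe does not reveal its content. A correctly labelled syringe of the wrong strength would pass.

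Study drug use to the end of POD 1, 2 and 3 is also a secondary endpoint (section 1.3). If the syringe is counted in it, each active patient's total depends on which strength was given.

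**Working it through.** **Inputs**

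- Bolus volume: 20 ml (section 7.2.3).
- Bolus strength: 0.5% (section 7.2.3) or 0.2% (section 7.4.6.3).
- Automatic pump bolus: 15 ml of 0.2% every 3 hours (section 7.2.3).
- Lower weight limit: 60 kg (section 3.1). Section 3.1 sets no upper limit; 120 kg is the top of the range that section 7.2.3 gives for standard dosing of the automatic boluses, and is used here only for scale.

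The plan states no milligram figure for the bolus, so there is none to reproduce.

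**Conversion.** A 1% solution is 10 mg/ml, so 0.5% = 5 mg/ml and 0.2% = 2 mg/ml. Dose = volume × concentration.

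| | Section 7.2.3 | Section 7.4.6.3, at 20 ml |
|---|---|---|
| Strength | 5 mg/ml | 2 mg/ml |
| Bolus dose | 20 × 5 = 100 mg | 20 × 2 = 40 mg |
| Per kg at 60 kg | 100/60 = 1.67 mg/kg | 40/60 = 0.67 mg/kg |
| Per kg at 120 kg | 100/120 = 0.83 mg/kg | 40/120 = 0.33 mg/kg |

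**Gap.** 100 − 40 = 60 mg; 100/40 = 2.5. One automatic bolus is 15 × 2 = 30 mg, so the gap equals 60/30 = 2 automatic boluses, or 6 hours of automatic dosing.

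**Could volume reconcile the two?** To deliver 100 mg at 2 mg/ml the syringe would need 100/2 = 50 ml. No such volume is stated, and section 7.2.3 says 20 ml.

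**Could another section settle it?** Sections 7.4.1 and 7.4.2 name only 0.2% and give no bolus dose. Section 7.4.6.1 mentions a supply of ropivacaine without a strength. Section 7.4.6.5 refers back to section 7.2 only for concomitant therapy. Section 7.2.5 says study order sets will be created, but their content is not given. None of these resolves the conflict.

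**The case against.** The best case on the other side accepts the contradiction and argues that it matters little.

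First, section 7.2.3 is the only place that gives the bolus both a volume and a strength, and it separates bolus from pump. The sentence in section 7.4.6.3 may simply be loose drafting that covers syringe and cartridge together. That is plausible, and it makes 0.5% the likelier intention. It does not show what was intended or dispensed, and the sentence with the other strength sits in the preparation section.

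Second, the order sets may carry the right dose, and no section says the pharmacy works from section 7.4.6.3 alone. That is true. But the order sets are to be written for this protocol, whose text conflicts, so they do not cure the problem.

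Third, the 2.5-fold ratio applies to the loading dose, not to exposure when the primary outcome is measured. If the pump starts at about 07:30 on the day of surgery (an assumption), about 8 automatic boluses (8 × 30 = 240 mg) come before the POD 1 assessment. Cumulative drug is then about 340 mg versus 280 mg before demand doses, a ratio of 340/280 = 1.21. This stands, and it is why no effect on the primary result is claimed. The sample size in section 8.2 uses none of these inputs.

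Fourth, staff who must stay blinded cannot verify strength at the bedside; that task falls to the unblinded pharmacy. This is also true. The bedside check is not defective. It means only that an error made at preparation would not be caught later by that check, so the instruction for preparation has to be right.

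Fifth, the pump lock-out adds nothing firm. The pump stops "if the total dose of study drug reaches 770mg", and the document does not say whether the syringe bolus counts. If it counts, automatic boluses alone reach the cap after (770 − 100)/30 × 3 = 67 h or (770 − 40)/30 × 3 = 73 h. If it does not, the time is 770/30 × 3 = 77 h under both readings. The conclusion does not rest on this.

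**Conclusion.** The concern holds. Two current sections give different strengths for the active arm's starting bolus, and nothing in the document reconciles them. The size is 100 mg versus 40 mg, a difference of 60 mg and a ratio of 2.5. The only assumption behind the 40 mg is that the 20 ml of section 7.2.3 also applies to the syringe in section 7.4.6.3.

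This is an internal inconsistency in the dose, not a miscalculation. Randomization, the saline control, the sample size and the planned test are the same under either reading. Which strength is right, and which was dispensed, cannot be read from the document. It should still be treated as a required correction, because following the preparation section as written gives a different loading dose from the procedures section.

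**What to change.** Amend section 7.4.6.3 so that syringe and cartridge are described separately: the syringe with one strength and its volume (0.5% in 20 ml if section 7.2.3 is what was intended), and the cartridge with 0.2%. Use the same words in sections 7.2.3, 7.4.1 and 7.4.2 and in the study order set. The choice of strength is the sponsor's.

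Check the pharmacy's preparation records. If patients have already been treated, report the strength they received.

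The same amendment could usefully say whether the syringe bolus counts toward the 770 mg lock-out and toward the study-drug-use endpoint; that is a clarification and not part of the error.

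The cost is a wording amendment and a records check. Design, sample size and analysis do not change.

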### **7.4.6.4 Return or Destruction of the Test Article**

Study drug will be discarded as per standard procedures.

### **7.4.6.5 Prior and Concomitant Therapy**

See section 7.2 Study Procedures for full details on concomitant medical therapy administered both during the operation, perioperative period and at hospital discharge.

## **8.0 Subject Numbers and Statistical Plan**

### **8.1 Number of Subjects**

40 patients, 20 per group.

### **8.2 Sample size determination**

A total of N=17 patients in each group (N=34 total) yields 80% power to detect a 2-point mean decrease in pain scores using a 2-sided t-test conducted at a significance level of 0.05 and assuming that the standard deviation (in each group) is 2. The standard deviation was selected to be slightly smaller than the standard deviation (2.5) under the assumption that all pain scores are equally likely (uniform

distribution). In order to account for potential patient withdrawals from the study (see section), we have expanded the number to 20 patients randomized in each group.

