### 1.2 Primary Study Endpoints

1. Pain scores using the Visual analogue scale (VAS) 0-10 on postoperative day 1. (VAS scale document attached)

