## 2.2 Previous Data

Recently, the erector spinae plane block (ESPB) has been described in multiple case studies. In 2016, Mauricio and colleagues presented ESPB as a novel analgesic technique in thoracic neuropathic pain. The authors used the proposed block successfully to manage thoracic pain in 4 patients presenting with chronic thoracic pain (2 cases) and postoperative pain control following video assisted thoracoscopic procedures (2 cases). The same group has also utilized the same technique for postoperative pain control following ventral hernia repair and thoracotomy.

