### **3.3.2 Follow-up for withdrawn subjects**

If subjects need to be withdrawn from the study based on the above reasons, they will transition to following the clinical standard of care that is medically required for their particular situation. The block that is in place will be unblinded to the physician and patient. Unblinding will help the physician and patient understand if it may be worth trying to continue with the block in such circumstances as a means of pain control. Continuation with the blinding procedures could only delay achievement of adequate pain control and removal of unnecessary hardware, if the block ends up containing the control—normal saline. The remainder of the hospital course for these withdrawn subjects will continue according to standard medical practice. Their course will continue to be tracked for research purposes and they will be included and reported in the study results.

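### The benchmark used to justify the planning SD of 2 is miscalculated: equally likely scores on a 0-10 scale have an SD of 2.89 or 3.16, not 2.5

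*Combined protocol and SAP*

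**What the plan says.** The primary endpoint in section 1.2 is "Pain scores using the Visual analogue scale (VAS) 0-10 on postoperative day 1", and section 7.2.5 describes the same 0-10 scale as it is administered on the ward.

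Section 8.2 states that "A total of N=17 patients in each group (N=34 total) yields 80% power to detect a 2-point mean decrease in pain scores", with a two-sided t-test at the 0.05 level and "assuming that the standard deviation (in each group) is 2". The reason given for that SD is that it was "selected to be slightly smaller than the standard deviation (2.5) under the assumption that all pain scores are equally likely", which the text identifies as a uniform distribution. The number randomized is then raised to allow for withdrawals; section 8.1 gives "40 patients, 20 per group".

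No pilot data, published variability or chart review is cited for the SD. The account of earlier work in section 2.2 opens with "Recently, the erector spinae plane block (ESPB) has been described in multiple case studies" and reports no VAS mean or SD. Power is not shown for any other SD.

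**The concern.** The SD is the least certain input to the sample size, and the plan offers one yardstick for judging it. That yardstick is a mathematical quantity that can be checked from the scale alone, and the value given does not match a 0-10 scale. The error makes the chosen SD look closer to the benchmark than it is.

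Two things are at stake. A reader who compares 2 with 2.5 will think the planning value better supported than it is. And if the primary comparison is null, the stated 80% may be taken as evidence that a 2-point effect was adequately tested for, with no indication of how far that figure depends on an SD whose only justification contains an error.

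**Working it through.** **Inputs.** From section 8.2: difference 2 points, SD 2 per group, two-sided alpha 0.05, t-test, 17 per group, benchmark SD 2.5. From section 8.1: 20 per group randomized. From sections 1.2 and 7.2.5: score range 0 to 10.

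**Step 1. Reproduce the plan's sample size.** For a two-sample t-test with n per group, power comes from the noncentral t distribution with 2n − 2 degrees of freedom and noncentrality difference / (SD × √(2/n)).

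- n = 17: noncentrality = 2 / (2 × √(2/17)) = 2.915, df = 32, power = 80.7%.
- n = 16: power = 78.1%.

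So 17 per group is the smallest number that reaches 80%. The plan's figure is correct for its stated SD.

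**Step 2. Recompute the benchmark.**

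- Continuous uniform on 0 to 10: SD = (10 − 0)/√12 = 2.887.
- Whole numbers 0 to 10, eleven equally likely values: SD = √((11² − 1)/12) = √10 = 3.162.

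Starting the scale at 1 does not give 2.5 either: continuous 1 to 10 gives 9/√12 = 2.598, and whole numbers 1 to 10 give √(99/12) = 2.872. The value 2.5 equals the range divided by 4, and also the mean absolute deviation of a continuous 0-10 uniform, but neither is the SD of that distribution.

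**Step 3. Gap between the planning SD and the benchmark.**

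- Against 2.5: 1 − 2/2.5 = 20.0%.
- Against 2.887: 1 − 2/2.887 = 30.7%.
- Against 3.162: 1 − 2/3.162 = 36.8%.

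**Step 4. Sensitivity of power to the SD** (same formula, difference 2):

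| SD | Power, 17 per group | Power, 20 per group | Difference detectable with 80% power, 17 / 20 per group |
|---|---|---|---|
| 2 | 80.7% | 86.9% | 1.98 / 1.82 |
| 2.5 | 61.9% | 69.3% | 2.48 / 2.27 |
| 2.887 | 50.0% | 57.0% | 2.86 / 2.62 |
| 3.162 | 43.2% | 49.6% | 3.13 / 2.87 |

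The fall from 80.7% to 61.9% (86.9% to 69.3% at 20 per group) reflects the plan's open choice of 2 over its own 2.5. Only the further fall below 61.9% (or 69.3%) is attributable to the miscalculated benchmark.

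**Step 5. Largest SD that keeps 80% power for a 2-point difference.** The detectable difference is proportional to the SD, so the limit is 2 × 2/1.982 = 2.018 with 17 per group and 2 × 2/1.818 = 2.200 with 20 per group.

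**Step 6. A benchmark that permits the planned shift.** If both arms were uniform over the whole scale, their means would be equal and no 2-point difference could exist. As an illustration of my own, not the plan's, take one arm uniform on 0 to 8 and the other on 2 to 10.

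- Continuous: SD = 8/√12 = 2.309, power 68.7% with 17 per group and 76.1% with 20.
- Whole numbers: SD = √((9² − 1)/12) = 2.582, power 59.1% and 66.5%.

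**The case against.** The strongest reply is that the wrong figure enters no calculation. The sample size is computed from an SD of 2, which is openly stated, and it reproduces. The uniform distribution is a deliberately wide benchmark that a planner would expect to go below, so raising it from 2.5 to 2.89 is not evidence that 2 is too small. Once the planned shift is allowed, the illustration in step 6 gives SDs of 2.31 and 2.58, which lie on either side of 2.5. All 20 per group may also be analysed, since section 3.3.2 says of withdrawn subjects that "they will be included and reported in the study results"; power at SD 2 is then 86.9%. A narrow margin around the planning SD is normal when N is the smallest that reaches 80%. And the final t-test uses the observed SD, so inference is unaffected.

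Much of this stands. The trial is not shown to be underpowered, the analysis is unaffected, and the 3.16 figure applies only if whole numbers are recorded, which depends on the VAS form attached to the protocol and not seen here.

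It does not rescue the sentence in section 8.2. That sentence refers to all pain scores being equally likely, which on this scale means the full 0-10 range, and 2.5 is not the SD of that distribution. Being near the SD of a different, narrower distribution does not make it correct. Since this comparison is the only reason offered for the planning SD, once it is corrected the value of 2 has no stated support.

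**Conclusion.** The concern holds. The benchmark in section 8.2 should be 2.89 for a continuous 0-10 score, or 3.16 for whole numbers, and the planning SD is 31% to 37% below it, not 20%. To call it a small step down is wrong as written, and the error favours the planning assumption.

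The power statement is correct as a conditional statement: 80.7% with 17 per group if the SD is 2. It falls below 80% once the SD exceeds 2.02 (17 analysed) or 2.20 (20 analysed). The power values at larger SDs assume a two-sided t-test at 0.05, a true difference of 2 points and equal SDs in the two arms. They show sensitivity and do not predict this trial's SD. This should be fixed, because it concerns the sole justification of an input that sets the sample size.

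**What to change.** In section 8.2, replace 2.5 with 2.89 (or 3.16 if the VAS form records whole numbers), and remove the wording that presents 2 as only a little below the benchmark. Then do one of two things: cite data that support an SD of 2 for POD 1 pain scores in a comparable population, or state power as conditional on the SD. Suitable text for the second option:

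> With 17 (20) patients per group analysed, power to detect a 2-point difference is 81% (87%) if the SD is 2, 62% (69%) if it is 2.5, 50% (57%) if it is 2.89 and 43% (50%) if it is 3.16. Power is at least 80% only if the SD is no more than 2.02 (2.20). These are sensitivity values, not forecasts.

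The cost is a change of wording in one section and a less favourable power statement. No additional patients are needed, and the test and significance level stay as they are.
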